- Concurrent pregnancy-related maternal medical conditions or pregnancy complications, including
 - Preterm labor
 - Placenta previa
 - Placental abruption
 - Incompetent cervix
 - Ectopic pregnancy
 - Molar pregnancy

Maternal Exposures during Pregnancy

Collected from HCP(s) – obstetric and prescriber, if needed – at enrollment, end of 2nd trimester, and pregnancy outcome; at the end of the 2nd trimester and pregnancy outcome, HCPs are asked only for updates to the data previously reported

- Exposure to tirzepatide, including indication/reason for use (approved according to label in country of residence), dose, route, frequency, and dates/duration of exposure, if available
- Exposure to other drugs or biological products (including prescription and non-prescription drugs, dietary/herbal supplements (including folic acid and prenatal vitamins), vaccines (including COVID-19), known teratogens (see Section 9.11.1.1.4), and investigational medications), including indication/reason for use, dose, route, frequency, and dates/duration of exposure, if available
- Exposure to tobacco, alcohol, marijuana, or recreational or illicit drugs, including timing of exposure, if available

Pregnancy Outcome Information

Collected from HCP(s) – obstetric and pediatric, if needed – at or after pregnancy outcome

- Pregnancy outcome (for each fetus, classified in one of the following mutually exclusive categories: SAB, stillbirth, induced abortion, and live birth)
- Maternal outcomes: pregnancy induced hypertension, pre-eclampsia, eclampsia, gestational diabetes, maternal cardiac disease, HG, and inadequate GWG.
- Date of pregnancy outcome
- Gestational age at pregnancy outcome
- Fetal/infant sex
- Fetal/infant weight, length, and head circumference at pregnancy outcome (when available)
- Labor type (spontaneous or induced)
- Route of delivery (i.e., vaginal delivery, assisted vaginal delivery, planned caesarean delivery, or emergency caesarean delivery)
- Delivery complications
- 5 Apgar scores
- Congenital malformations (major and minor), including post-mortem findings for fetal losses and assessment of potential contributing factors
- Maternal weight at (just prior to) pregnancy outcome
- For live births, prolonged hospitalization after delivery and reason
- For a non-induced fetal loss (SAB, stillbirth), factors that may have had an impact on the fetal loss and attribution

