9.11.1.3. Prospectively Enrolled Versus Retrospectively Enrolled Participants

The registry will encourage prospective registration; however, retrospective enrollment in the registry will be permitted. A prospectively enrolled participant is defined as a pregnant individual who enrolls or makes initial contact with the registry prior to pregnancy outcome. A retrospectively enrolled participant is defined as a pregnant individual who enrolls or makes initial contact with the registry after the pregnancy outcome (e.g., live birth, stillbirth, SAB, induced abortion) has occurred (up to 12-months after pregnancy outcome).

Retrospectively enrolled participants can introduce bias toward the reporting of more unusual and severe outcomes and are less likely to be representative of the general population than prospectively enrolled participants. Therefore, retrospectively enrolled participants will be excluded from the main analysis population but will be included in supplementary analyses.

Diagnostic prenatal tests (e.g., ultrasound to scan for structural defects at approximately 20 gestational weeks, chorionic villus sampling, and amniocentesis) can determine with high accuracy whether a fetus has a structural or chromosomal abnormality. Therefore, inclusion of individuals who have had diagnostic prenatal testing in the analysis population may introduce bias. To examine this potential bias, a sensitivity analysis that applies a stricter definition of prospective enrollment will be conducted. For this analysis, individuals who enroll or make initial contact with the registry prior to diagnostic prenatal testing (and pregnancy outcome) will be considered prospectively enrolled, and individuals who enroll or make initial contact with the registry after diagnostic prenatal testing, regardless of the results, will be considered retrospectively enrolled in addition to individuals who enroll after pregnancy outcome. In this sensitivity analysis, the outcomes of individuals who enroll prior to diagnostic prenatal testing will be compared with those of individuals who enrolled after diagnostic prenatal testing.

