- For SAB and preterm birth, prevalence will be calculated among the subset of individuals who are enrolled in the registry prior to 20 and 37 gestational weeks, respectively. Additionally, for these time-to-event outcomes, data will be censored at appropriate time points: 20 gestational weeks for SAB and 37 gestational weeks for preterm birth.
- For pregnancy complications prevalence will be calculated according to the following assessment windows:
 - Pregnancy induced hypertension reported for the first time among participants after 20 weeks gestation.
 - Pre-eclampsia/eclampsia reported among participants after 20 weeks of gestation.
 - New-onset gestational diabetes reported among participants at any time during pregnancy
 - Inadequate maternal weight gain reported among participants at any time during pregnancy.
 - HG reported among participants anytime during pregnancy.
- Prevalence will be calculated at multiple time points for postnatal growth deficiency, rapid infant weight gain, and infant developmental delay will be assessed at 4 months (± 2 weeks) and 12 months (± 2 weeks) of infant age. At each time point, prevalence will be calculated among infants with data available for the particular outcome at that time point. If there is no assessment available at 4 and/or 12 months, available data will be evaluated based on the actual time of assessment (e.g., if the infant was measured at 6 months, these data will be compared to the values appropriate for a 6-month-old infant based on the growth charts). However, only development at 4 and 12 months will be reported as study outcomes, results from other time points will be reported in a separate category.

The unweighted univariate regression will be used to compare the crude (unadjusted) RRs for all outcomes. Adjusted methods will incorporate weights estimated using the IPTW method to balance the cohorts with regard to observable covariates (Section 9.11.2.4). A weighted generalized linear model using a binomial family and a log (relative risk) link will be employed to estimate an adjusted relative risk.

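### Maternal complications diagnosed before enrollment count as main-analysis outcomes, and no planned row shows how far their risk ratios depend on who chose to enroll

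*Protocol*

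**What the plan says.** Section 9.11.1.3 (numbered 9.11.1.1.3 in the table of contents) sets the entry rule for the main analysis: "A prospectively enrolled participant is defined as a pregnant individual who enrolls or makes initial contact with the registry prior to pregnancy outcome". It excludes later enrollees on the ground that "Retrospectively enrolled participants can introduce bias toward the reporting of more unusual and severe outcomes".

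Section 9.11.2.2 then fixes the assessment windows for the maternal complications:

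- Gestational diabetes: "New-onset gestational diabetes reported among participants at any time during pregnancy".
- Pregnancy-induced hypertension: "Pregnancy induced hypertension reported for the first time among participants after 20 weeks gestation".
- Pre-eclampsia and eclampsia: "Pre-eclampsia/eclampsia reported among participants after 20 weeks of gestation".
- Hyperemesis gravidarum: "HG reported among participants anytime during pregnancy".

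In Table 9.7 the denominators are the whole analysis population (gestational diabetes, hyperemesis) or everyone who reached 20 weeks (the three hypertensive outcomes). The table's sensitivity rows for the four secondary outcomes add only a requirement for pregnancy outcome data. Hyperemesis has no sensitivity row. Enrollment timing enters only for spontaneous abortion and preterm birth, where "prevalence will be calculated among the subset of individuals who are enrolled in the registry prior to 20 and 37 gestational weeks".

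Section 9.6 collects data cumulatively over the pregnancy, Section 9.6.4 lets women enroll themselves, and Section 9.13 expects some to join much later in pregnancy.

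**The concern.** Section 9.11.1.3 distrusts participants who join once the outcome is known. A woman who joins at 32 weeks with diagnosed gestational diabetes or pre-eclampsia is in that position for that outcome, yet she enters the main numerator. Because data reach back over the whole pregnancy, her earlier diagnosis is captured and counted.

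This is harmless if the decision to enroll is unrelated to the complication. With voluntary self-enrollment that cannot be assumed. Nor is the incentive clearly the same in each cohort: Section 9.6.3.1 recruits tirzepatide-exposed women first and tailors the comparator campaign later, and several awareness channels (product website, contact centre, patient assistance program, prescribing information) are linked to tirzepatide or its sponsor. The risk ratios for four secondary outcomes and for hyperemesis could then partly reflect enrollment behaviour.

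Section 9.13 discusses left truncation and general representativeness. It does not discuss complications already present at enrollment being counted as events.

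**Working it through.** **Text check.** For each outcome, does the plan require enrollment before onset?

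| Outcome | Counted when | Denominator | Enrollment condition |
|---|---|---|---|
| Gestational diabetes | any time in pregnancy | analysis population | before pregnancy outcome only |
| Hyperemesis | any time in pregnancy | analysis population | before pregnancy outcome only |
| Pregnancy-induced hypertension, pre-eclampsia, eclampsia | after 20 weeks | reached 20 weeks | before pregnancy outcome only |
| Spontaneous abortion | before 20 weeks | enrolled before 20 weeks | yes |
| Preterm birth | before 37 weeks | enrolled before 37 weeks | yes |

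**Size.** The protocol gives no figure for enrollment timing or for selection on complications, so there is no stated result to reproduce. What follows is an illustration.

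Inputs from the protocol:

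- Reference prevalences (Table 9.4): gestational diabetes 6.9%, pregnancy-induced hypertension 6.5%, pre-eclampsia 3.8%, hyperemesis 2.5%.
- Cohort size (Section 9.9.1): 265/0.9/0.9/0.9 = 363.5, so 364 enrolled, which agrees with the protocol. After the 10% exclusion, 364 × 0.9 ≈ 328 remain per cohort.

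Assumptions, not in the protocol:

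- s, the share of cases already diagnosed when the woman could enroll: 0.25, 0.5 or 1.0.
- k, how much more likely those women are to enroll: 1.5, 2 or 3.

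Formulas: the relative enrollment of cases is m = 1 + s(k − 1), and the observed prevalence is p·m / (p·m + 1 − p).

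*Enrichment in one cohort only, true risk ratio 1, s = 0.5, k = 2, so m = 1.5:*

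- Gestational diabetes: 0.1035/(0.1035 + 0.931) = 10.0%; ratio 1.45.
- Pregnancy-induced hypertension: 0.0975/(0.0975 + 0.935) = 9.4%; ratio 1.45.
- Pre-eclampsia: 0.057/(0.057 + 0.962) = 5.6%; ratio 1.47.
- Hyperemesis: 0.0375/(0.0375 + 0.975) = 3.7%; ratio 1.48.

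Over the full grid the spurious ratio runs from 1.12 (s = 0.25, k = 1.5) to between 2.64 and 2.86 (s = 1.0, k = 3). For gestational diabetes with 328 per cohort, an unweighted two-sided test of two proportions at 0.05 would be significant with probability 0.06 to 0.99 over the grid, and 0.30 in the middle case.

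*Equal enrichment in both cohorts:* a true ratio of 1 stays at 1.00. A true ratio of 3 for gestational diabetes with m = 2 becomes [0.414/(0.414 + 0.793)] / [0.138/(0.138 + 0.931)] = 0.343/0.129 = 2.66.

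Eclampsia, at 0.281%, gives 328 × 0.00281 ≈ 0.9 expected cases per cohort, so its ratio will be uninformative either way.

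The sample sizes for gestational diabetes and pregnancy-induced hypertension at a relative risk of 3 in Table 9.4 (115 and 107) appear interchanged for the prevalences given. This does not matter here: either prevalence gives 1.45.

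**The case against.** Several points on the other side have weight.

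- *Dates.* A reader might infer that events before and after enrollment cannot be separated, because Section 9.8 lists "Maternal outcomes: pregnancy induced hypertension, pre-eclampsia, eclampsia, gestational diabetes, maternal cardiac disease, HG, and inadequate GWG" with no onset date. That goes too far. Section 9.11.2.8 has an imputation rule for start dates of medical conditions, Section 9.8 records first contact and consent, and relevant medical conditions are collected from enrollment onward. It remains unconfirmed that start dates are captured for these five outcomes.
- *The rule for spontaneous abortion and preterm birth.* A reader might infer that the plan breaks its own rule. It does not quite. That rule requires enrollment before the window closes, not before it opens. For hypertensive outcomes, whose window runs to delivery, the literal equivalent is the existing definition. Requiring enrollment before onset is a new, stricter condition, supported by the plan's reason for excluding retrospective participants.
- *The planned check.* Sections 9.11.1.3 and 9.11.2.7 compare outcomes in women enrolling before and after diagnostic prenatal testing. With a scan at about 20 weeks this covers much of the hypertensive problem. It does not isolate hyperemesis that preceded the test, and it is not keyed to the complication.
- *Adjustment.* Gestational age at enrollment is a candidate covariate in Section 9.7.4. Adjusting for it does not remove selection on the diagnosis itself.
- *Full ascertainment.* Dropping diagnosed women while keeping late, still-undiagnosed enrollees shortens time at risk and understates prevalence. Restricting also costs sample in a registry whose feasibility estimate (305) is below its target (364). This argues against making the restricted version the main analysis.

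**Conclusion.** The point stands in a conditional form. As written, the main rows count these five complications regardless of whether they were known before enrollment. If diagnosed women over-enroll, each affected cohort's prevalence is too high.

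A reader might go further and infer that the tirzepatide risk ratios will be inflated. The documents do not support that. A shift from a true null needs over-enrollment to differ between cohorts. Tirzepatide-first recruitment makes this plausible, but Section 9.6.3.1 also says comparator recruitment will be tailored for comparability, and data collection is identical across cohorts. Neither size nor direction is known. The middle-case ratios of 1.45 to 1.48 and the range of about 1.1 to 2.9 rest wholly on assumed values of s and k and on enrichment in one cohort only. With equal enrichment the distortion is toward 1.

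The affected outcomes are four secondary outcomes and one exploratory outcome, all with nominal p-values under Section 9.11.2. The primary malformation analysis is untouched. A modest, pre-specified addition is warranted; replacing the main analysis is not.

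**What to change.** Keep the all-enrolled rows of Table 9.7 as main and add one pre-specified sensitivity row per outcome:

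- **Pregnancy-induced hypertension, pre-eclampsia, eclampsia:** women enrolled before 20 weeks. As these outcomes are counted only after 20 weeks, all such women join before the outcome can be counted.
- **Gestational diabetes, hyperemesis:** women free of the diagnosis at enrollment, with delayed entry on the gestational-age scale or an enrollment cutoff stated in advance, so that shortened time at risk is handled.

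State whether first contact or consent is the reference date, since Section 9.11.1.3 accepts either. For each outcome, report by cohort the number of events with onset before enrollment; a difference between cohorts would be the direct warning sign. Confirm that the condition start dates implied by Section 9.11.2.8 are captured for these five outcomes, and add a date field for any that lack one.

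Cost: up to five date fields and five table rows, with smaller denominators and wider intervals in those rows. The main analysis and sample size do not change. It is best settled early, because onset dates not recorded at the time may be hard to recover in a registry collecting data until 2035.

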9.11.2.3. Demographic and Baseline Characteristics

Demographic and baseline characteristics will be summarized with descriptive statistics, and balance between cohorts will be assessed using standardized differences. These data will be presented before and after balancing using the IPTW method (Section 9.11.2.4). In addition, within each cohort, those included in the main analysis population will be compared with those excluded from the main analysis population for being lost to follow-up, retrospectively enrolled, exposed to teratogens or investigational medications during pregnancy, or having already been included in the analysis population for a prior pregnancy.

9.11.2.4. Adjustment for Covariates and Confounders

Because of the real-world nature of the study, there is a high potential for imbalance between the cohorts regarding observed covariates. To address this imbalance, adjusted analyses that employ the IPTW method will be conducted in each of the two comparison sets separately: tirzepatide exposed vs. AOM active comparator and tirzepatide exposed vs. AOM unexposed comparator. The IPTW method is widely used in observational studies to adjust for confounding due to differences between comparator groups that arise in observational data.⁹⁹⁻¹⁰¹

The IPTW allows us to estimate an average treatment effect, which is interpreted as the effect of treatment in the entire study population.¹⁰²

The IPTW approach assigns a weight to each participant based on observed demographical and clinical covariates:

- For the tirzepatide cohort, the weight is equivalent to the inverse of the propensity score (PS; i.e., the probability of the participant belonging in their assigned cohort).
- For each of the comparator cohorts, the weight is equivalent to the inverse of 1 minus the PS.

PS, the probability of treatment assignment conditional on observed baseline characteristics, will be derived with logistic regression. There is a large number of potential confounders, as described in Section 9.7.4. To ensure key clinical variables are included in the PS estimation, a set of covariates to be included in the PS model will be prespecified in the SAP, based on causal diagrams along with the literature and clinical expertise. Examples of such variables are age and pregnancy history. These variables will be included in the PS model even if balanced between the treatment cohorts due to their significance as risk factors for the outcome of interest. Other variables will be inspected for balance between the treatment cohorts before and after applying the IPTW. Covariates that remain imbalanced between the treatment cohorts will be added in the PS model, and balance between the treatment cohorts will be re-inspected. Any covariates that continue to show imbalance may be added to the final outcome model for regression adjustment. The PS estimation and assessment of covariate balance will be conducted without examining the study outcomes.

This method can occasionally generate extremely large weights for a small number of participants, creating unstable results that are highly dependent on a small number of participants. To address this issue, stabilized weights will be used. Stabilized weights for each

treatment cohort are created by multiplying the weight of the respective treatment cohort (i.e., $1/PS$ for the tirzepatide cohort and $1/[1-PS]$ for the comparator cohort) by the marginal probability of receiving the treatment in the respective treatment cohort. Distribution of stabilized weights will be inspected with the summary statistics (mean, standard deviation, minimum, and maximum) and histograms to ensure there are no extreme weights. To reduce the influence of extreme weights, the stabilized weights will be truncated at the first and 99th percentiles. A sensitivity analysis will use trimming to assess any impact of excluding extreme weights.

Once the PSs are estimated, we will assess the PS distribution of each treatment group for the imbalance between two cohorts (the extent of their overlap) and the presence of extreme PSs. If after applying stabilized weights, the cohorts remain unbalanced, other methods may be considered, such as revising the PS model by including interaction or non-linear quadratic terms, using overlapping weights (e.g., if the positivity assumption is being violated), or further adjustment in the regression model for the unbalanced baseline characteristics. Overlapping weights emphasize the target population with the most overlap in observed characteristics between treatments, by continuously down-weighting the units in the tails of the PS distribution.¹⁰³

The weights will be incorporated into the regression model (aka weighted regression) for estimating adjusted RR; covariates that remain not well-balanced after the final set of weights are created (defined as having an absolute standardized difference of greater than 10% after weighting) will be further adjusted for through inclusion into the regression model as a covariate. In addition, a high proportion of missing data for a covariate could make application of the IPTW method more challenging, as weights can be estimated only for participants with known values. If there is a high degree of missingness among clinically important covariate data, multiple imputation of these variables will be considered where the variables are assumed missing at random. Variables whose missingness would trigger additional sensitivity analyses with imputation will be indicated in the SAP. For the imputation, Rubin's rules will be applied, and the imputed values will be used for weight estimation by estimating the treatment effect for each imputed dataset and then averaging them into a single treatment effect estimate.^{104,105} Further details on this will be provided in the SAP.

It is also acknowledged that IPTW procedure could result in loss of effective sample size compared to the actual (apparent) sample size if the overlap between tirzepatide exposed cohort and the comparator cohorts is small. Once sufficient data have become available (approximately 100 patients per cohort), the PS distributions will be assessed to determine whether there is sufficient overlap between the cohorts (the 2 treatment comparisons treated separately) to achieve the desired power in the analysis. The variance inflation factor will be computed as the ratio of the actual to effective sample size, and the required sample size will be updated by multiplying the required sample size (approximately 364 patients per cohort) by the variance inflation factor.

9.11.2.5. Stratified Analyses

Where sample size permits, stratified/subgroup analyses of all outcomes will be conducted that consider the timing of exposure (earliest trimester of exposure), extent of exposure (cumulative dose during pregnancy or relevant exposure window), country, BMI category at conception, maternal age group at conception (<18 years, 18 to 34 years, 35 to 44 years, and 45 to 50 years), and maternal race and ethnicity.

